All initial reports of pregnancy in a subject and pregnancies in partners of male subjects included in the study must be reported to [redacted] by the investigator within

24 hours of knowledge of the event, using a pregnancy form. Any subject who becomes pregnant during the study must be promptly withdrawn from the study (not applicable if subjects are male). Spontaneous abortion is considered an SAE and will be reported as such.

The investigator will contact the subject at the expected time of delivery for follow-up on the pregnancy outcome. Abnormal pregnancy outcomes are considered SAEs and must be reported using the SAE Form.

8.8.1.2.1.6 Reporting Serious Adverse Events to Competent Authorities/ Ethics Committees

██████████ assumes responsibility for appropriate reporting of AEs to the regulatory authorities. ██████████ will also report to the investigator(s) all SAEs that are unlisted (unexpected) and associated with the use of the study medication. The investigator(s) (or ██████████ where required) must report these events to the appropriate IEC/IRB that approved the protocol unless otherwise required and documented by the IEC/IRB.

AE reporting, including suspected unexpected serious adverse reactions, will be carried out in accordance with applicable local regulations.

After termination of the clinical study (last subject last contact in the study), any unexpected safety issue that changes the risk benefit analysis and is likely to have an impact on the subjects who have participated in it, will be reported by the sponsor, ██████████ as soon as possible to the competent authority(ies) concerned together with proposed actions.

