control methods must have consistently used the same method for at least three months prior to study dosing. Hormonally-based contraceptives and barrier methods permitted for use in this protocol are as follows:

- Hormonal methods (subject must agree to use with a barrier method, preferably, with a male condom)
 - Oral contraceptives (either combined estrogen/progestin or progesterone only)
 - Injectable progesterone
 - Implants of levonorgestrel
 - Transdermal contraceptive patch
 - Contraceptive vaginal ring
- Barrier methods (subject must agree to use with a hormonal method)
 - Male or female condom, with or without spermicide
 - Diaphragm with spermicide
 - Cervical cap with spermicide
 - Sponge with spermicide
- All female subjects must also agree to refrain from egg donation and in vitro fertilization during study participation and for at least 35 days after the last study drug dose, or for at least 6 months for female subjects of childbearing potential who were taking concurrent MTX therapy, as indicated by the SmPC of MTX.

Participants and their providers must agree to adhere to the respective SmPC for concomitant csDMARDs used by the subject during the study. For example, if methotrexate is used as concomitant background medication during the clinical trial, subjects and investigators must agree to adhere to the methotrexate SmPC: “Women must not become pregnant during and at least 6 months after treatment with methotrexate and must therefore practice an effective form of contraception.”

3) Contraception for Male Subjects

It is theoretically possible that a relevant systemic concentration may be achieved in a female partner from exposure to the male subject’s seminal fluid. Therefore, male subjects with female partners of childbearing potential must agree to use condoms during study participation and for 90 days after the last study drug dose, or for at least 6 months for subjects who were taking concurrent MTX therapy, as indicated by the SmPC of MTX. Female partners of male study subjects should consider using one of the above methods of contraception as well. Male subjects must also agree to refrain from sperm donation during treatment and until at least 90 days after the end of dosing, or for at least 6 months for subjects who were taking concurrent MTX therapy, as indicated by the SmPC of MTX.

4) Unacceptable Birth Control Methods

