Birth control methods that are unacceptable include periodic abstinence (eg, calendar, ovulation, symptothermal, post-ovulation methods), withdrawal (coitus interruptus), spermicides only, and lactational amenorrhea method (LAM). Female condom and male condom should not be used together.

5) Procedures to be Followed in the Event of Pregnancy

Subjects will be instructed to notify the investigator if they become pregnant at any time during the study, or if they become pregnant within 35 days of last study drug dose, or within at least 6 months for subjects who were taking concurrent MTX therapy, as indicated by the SmPC of MTX. Subjects who become pregnant or who suspect that they are pregnant during the study must report the information to the investigator and discontinue all study drug and background therapy immediately. Subjects whose partner has become pregnant or suspects she is pregnant during the study are to report the information to the investigator.

Instructions for reporting pregnancy, partner pregnancy, and pregnancy outcome are outlined in Section [8.8.1.2.1.5](#).

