7.6. Other Safety Measures

A data listing will be provided for subjects who have positive or borderline urine or serum pregnancy test result during the study.

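### Appendix 13.8 gives male subjects no post-dose period for reporting a partner pregnancy, although it sets them a 90-day (at least 6 months with MTX) post-dose condom period and gives women matching periods

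*Protocol*

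**What the plan says.** Four parts of the protocol bear on this point.

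- **Male precaution (Appendix 13.8, item 3).** The reason given is: "It is theoretically possible that a relevant systemic concentration may be achieved in a female partner from exposure to the male subject’s seminal fluid". Men with partners of childbearing potential therefore "must agree to use condoms during study participation and for 90 days after the last study drug dose", or for at least 6 months if they took concurrent MTX. The 6 months is attributed to the MTX SmPC.
- **Notification by subjects (Appendix 13.8, item 5).** A female subject is to tell the investigator if she becomes pregnant during the study, "or if they become pregnant within 35 days of last study drug dose", or within at least 6 months with MTX. For men the rule is: "Subjects whose partner has become pregnant or suspects she is pregnant during the study are to report the information to the investigator". No post-dose period follows.
- **Reporting by the investigator (Section 8.8.1.2.1.5).** "All initial reports of pregnancy in a subject and pregnancies in partners of male subjects included in the study must be reported to" the safety contact within 24 hours of the investigator learning of them. No calendar limit is set. The section also provides for follow-up at the expected delivery date and treats abnormal outcomes as SAEs.
- **End of contact (Sections 8.7.3, 8.7.4 and 8.8.1.2.1.2).** The Follow-up Visit falls 2 weeks, plus or minus 4 days, after the Final Visit or EDV. Participation and AE recording both run to that visit.

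SAP Section 7.6 plans a listing of "subjects who have positive or borderline urine or serum pregnancy test result during the study". It does not mention partners.

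**The concern.** For women, item 5 asks for notification over the same post-dose period for which item 2 requires contraception: 35 days, or at least 6 months with MTX. For men the two periods part company. The protocol asks for precautions for 90 days or more, but the man's instruction to report stops with the study, and his own participation ends about two weeks after his Final Visit or EDV. No section explains the difference.

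Safety is the primary objective. Section 6.3.4 reports embryolethality and teratogenicity in rats and rabbits at exposures similar to human exposure at 200 mg q.d., and Appendix 13.8 says no safety margin has been identified. The outcome follow-up and SAE reporting in Section 8.8.1.2.1.5 can start only once someone tells the site. After the Follow-up Visit no contact is planned and the man's written instruction has lapsed, so a partner conception on, say, day 60 comes to light only if he volunteers it.

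**Working it through.** The plan states no figure of its own here, so the check is a comparison of periods and a day count.

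**Precaution and notification side by side (post-dose part)**

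| | Precaution | Subject's duty to notify |
|---|---|---|
| Women, no MTX | 35 days | 35 days |
| Women, MTX | at least 6 months | at least 6 months |
| Men, no MTX | 90 days | none stated |
| Men, MTX | at least 6 months | none stated |

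**Inputs**

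- Post-dose precaution W: 90 days, or 6 months with MTX (Appendix 13.8, item 3). Assumption: 6 months is 180 to 184 days.
- Day of last contact F: 14 ± 4, so 10, 14 or 18 days after the Final Visit or EDV (Section 8.7.3).
- Last dose date: the Final Visit or EDV date (SAP Section 3.5.1).
- The study is taken to end for each subject at his Follow-up Visit (Sections 8.7.4 and 8.8.1.2.1.2).

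**Formula.** Days with no duty on the man = W − F. Share of the post-dose period = (W − F) / W.

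| W | F = 10 | F = 14 | F = 18 |
|---|---|---|---|
| 90 | 80 (88.9%) | 76 (84.4%) | 72 (80.0%) |
| 180 | 170 (94.4%) | 166 (92.2%) | 162 (90.0%) |
| 183 | 173 (94.5%) | 169 (92.3%) | 165 (90.2%) |
| 184 | 174 (94.6%) | 170 (92.4%) | 166 (90.2%) |

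**Against the whole condom period.** Men must also use condoms throughout treatment, when the duty to report does apply. With y assumed years of treatment and F = 14, the uncovered share is (W − 14) / (365.25y + W):

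| y | W = 90 | W = 183 |
|---|---|---|
| 1 | 76/455.25 = 16.7% | 169/548.25 = 30.8% |
| 4 | 76/1551 = 4.9% | 169/1644 = 10.3% |
| 8 | 76/3012 = 2.5% | 169/3105 = 5.4% |

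So most of the post-dose period is uncovered, but a minority of the whole precaution period.

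**After alignment.** If the notification period equals W, the uncovered post-dose time is W − W = 0, as it already is for women.

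**The case against.** The strongest reply is Section 8.8.1.2.1.5. Item 5 refers the reader there for partner pregnancy, and the duty it places on the investigator has no time limit. A reader might infer from item 5 alone that a partner pregnancy after the study need not be reported, or that its outcome would be lost. The documents do not support that. Once the site knows, the 24-hour report applies, and the section's outcome follow-up and SAE text needs no repair. This stands, and it limits the point to what is asked of the subject. It does not remove the point, because the investigator's duty is triggered by knowledge. The protocol also gives women an explicit post-dose duty on top of the same section.

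Other limits also stand:

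- **Hazard.** A reader might take the 90 days as a period of established exposure. The protocol calls the seminal route only theoretically possible and sets a precaution period, not an exposure period. Section 6.3.3 reports half-lives of 4 and 5 hours in rats and dogs and nearly complete excretion within 24 hours. The teratogenicity data are not data on exposure through semen.
- **MTX.** The 6-month period rests on the MTX SmPC, so the 90 to 95% figure concerns a background-drug precaution and not filgotinib's own.
- **End of study.** Section 8.8.1.2.1.6 ties termination of the whole trial to the last subject's last contact. On that reading the gap narrows or closes for men who leave early, but remains for those who finish near the end. The wording should not leave this open.
- **SAP.** The protocol promises no listing of partner pregnancies, so SAP Section 7.6 contradicts nothing.

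**Conclusion.** The point holds as a gap in soliciting safety information. Followed exactly, Appendix 13.8 places no duty on a male subject to report a partner pregnancy for 72 to 80 of the 90 post-dose days (80 to 89%), or for about 162 to 174 days (90 to 95%) with MTX.

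These counts assume that the last dose is on the Final Visit or EDV date, that the study ends for each man at his Follow-up Visit, and that 6 months is 180 to 184 days. A man who stopped dosing before his EDV would have a gap shorter by the same number of days. The MTX case is unlikely to be rare: CL-203, the larger core study (about 595 subjects against about 280, Section 8.9.2), enrolled subjects on stable MTX. The documents do not give the number of men, so no count of affected subjects can be derived.

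The gap affects what safety information reaches the site. It changes no endpoint, estimate or sample size.

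**What to change.** Reconcile Appendix 13.8, items 3 and 5, with Section 8.8.1.2.1.5:

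1. In item 5, state that a male subject reports a partner pregnancy occurring during the study or within the post-dose precaution period that item 3 already applies to him.
2. Repeat that period in Section 8.8.1.2.1.5. Leave the outcome follow-up and SAE text as it is.
3. Carry the same sentence into the subject instructions.

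A listing of reported partner pregnancies with outcome beside the one in SAP Section 7.6 would be convenient, but is optional.

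The cost is one protocol sentence, its repetition in one section, and a line in the subject instructions. The downside is that a few reports may arrive after a subject's last visit and will have to be handled then. No contraception or dosing rule is touched.

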MedDRA	Medical Dictionary for Regulatory Activities
MST	MedDRA search listing
MTX	methotrexate
NRI	non-responder imputation
OC	observed case
PGA	physician's global assessment

PT	preferred term
PTM	placebo to match
PVE	pharmacovigilance & epidemiology department
Q1, Q3	first quartile, third quartile
q.d.	quaque die (each day)
RA	rheumatoid arthritis
RF	rheumatoid factor
SAE	serious adverse event
SAP	statistical analysis plan
SD	standard deviation
SDAI	simplified disease activity index
SF-36	36-item short form survey
SGA	subject's global assessment
SJC	swollen joint count
SMQ	standardized MedDRA query
SOC	system organ class
TEAE	treatment-emergent adverse event
TFLs	tables, figures, and listings
TJC	tender joint count
ULN	upper limit of normal
VAS	visual analog scale
WBC	white blood cell
WHO	World Health Organization

1. INTRODUCTION

This statistical analysis plan (SAP) describes the statistical analysis methods and data presentations to be used in tables, figures, and listings (TFLs) in the clinical study report (CSR) for study GLPG0634-CL-205. This SAP is based on the study protocol amendment 3 dated 15 March 2018 and the electronic case report form (eCRF). The SAP will be finalized before database finalization. Any changes made after the finalization of the SAP will be documented in the CSR.

1.1. Study Objectives

The primary objective of this study is as follows:

- To evaluate the long term safety and tolerability of filgotinib for the treatment of rheumatoid arthritis (RA)

The secondary objectives of this study are as follows:

- To evaluate the long-term efficacy of filgotinib
- To evaluate the long-term effects of filgotinib administration on subjects' disability, fatigue, and quality of life

GLPG0634-CL-205 data and the most current GLPG0634-CL-203 and GLPG0634-CL-204 data will be used in the analyses.

1.2. Study Design

This is a multicenter, open-label, long-term follow-up study in subjects with RA. An approximate total of 600 subjects will be enrolled in the study after they have completed one of the previous 2 core studies: (GLPG0634-CL-203 or GLPG0634-CL-204). All subjects will start the study at the same dose level (filgotinib 200 mg daily, administered either as 200 mg q.d. or as 100 mg b.i.d., depending on the dosing regimen (frequency of intake of active IMP) that was administered during the preceding core study). US males were limited to dosing with filgotinib 100 mg q.d. due to an FDA requirement based on a non-clinical testicular toxicity signal.

The investigator may decide to decrease the daily dose of filgotinib to 100 mg q.d. in case of intolerance or safety reasons. Subjects will return to the 200 mg filgotinib daily dose after the reasons for decreasing the dose have resolved, and at the investigator's discretion. Subjects can also continue on filgotinib 100 mg q.d. when deemed necessary by the investigator. Subjects coming from the GLPG0634-CL-204 study will be allowed to start MTX treatment, if deemed necessary according to the investigator's clinical judgment.

Subjects will enter the study at Entry Visit on Day -1, which will occur on the same day as the last visit from the previous core study (GLPG0634-CL-203 or GLPG0634-CL-204). Subjects

participating in the study will be requested to attend Quarterly Evaluation Visits (QEVs) every 12 weeks. If necessary, unscheduled visits can occur in between the scheduled study visits, for instance, in case the dose of study medication is to be adapted. In case of early withdrawal, an Early Discontinuation Visit (EDV) will be scheduled.

The duration of the participation and treatment for any subject in this study is expected to last for several years (from Entry visit to Follow-up Visit) and will be determined by the sponsor based on the following:

- Open label period (approximately 96 months).
- Marketing Application Approval/Withdrawal in Country of Residence.
- Applicable local reimbursement procedures are in place.

Sites will be notified once these criteria are met.

Following marketing, local (if applicable) regulatory and/or pertinent local reimbursement approval of the study medication, subjects should return to their next quarterly scheduled study visit as specified in the protocol. This visit will serve as a Final Visit and the subjects will be considered as having completed the treatment part of the study. At the end of the study, subjects will be requested to attend a Follow-up Visit approximately 2 weeks after the Final Visit.

The design of the study is presented in the following table:

Study 203		Roll over to Study 205
Week 1-12	Week 13-24	
Randomized to placebo	Responders(*) remain on placebo	Half of them are rerandomized to 200 mg q.d.
		Half of them are rerandomized to 100 mg b.i.d.
	Nonresponders: half of them are rerandomized to 100 mg q.d.	Assigned to 200 mg q.d.
	Nonresponders: half of them are rerandomized to 50 mg b.i.d.	Assigned to 100 mg b.i.d.
Randomized to 50 mg q.d.	Responders remain on 50 mg q.d.	Assigned to 200 mg q.d.
	Nonresponders assigned to 100 mg q.d.	Assigned to 200 mg q.d.
Randomized to 25 mg b.i.d.	Responders remain on 25 mg b.i.d.	Assigned to 100 mg b.i.d.
	Nonresponders assigned to 50 mg b.i.d.	Assigned to 100 mg b.i.d.
Randomized to 100 mg q.d.	Remain on 100 mg q.d.	Assigned to 200 mg q.d.
Randomized to 50 mg b.i.d.	Remain on 50 mg b.i.d.	Assigned to 100 mg b.i.d.
Randomized to 200 mg q.d.	Remain on 200 mg q.d.	Assigned to 200 mg q.d.
Randomized to 100 mg b.i.d.	Remain on 100 mg b.i.d.	Assigned to 100 mg b.i.d.
Study 204		Roll over to Study 205
Week 1-12	Week 13-24	
Randomized to placebo q.d.	All assigned to 100 mg q.d.	Assigned to 200 mg q.d.
Randomized to 50 mg q.d.	Responders remain on 50 mg q.d.	Assigned to 200 mg q.d.
	Nonresponders assigned to 100 mg q.d.	Assigned to 200 mg q.d.
Randomized to 100 mg q.d.	Remain on 100 mg q.d.	Assigned to 200 mg q.d.
Randomized to 200 mg q.d.	Remain on 200 mg q.d.	Remain on 200 mg q.d.

(*) responder: having a decrease of at least 20% in tender joint count (TJC)⁶⁸ and swollen joint count (SJC)⁶⁶ versus Baseline.

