Objectives:	
The primary objective is to evaluate the long-term safety and tolerability of filgotinib for the treatment of rheumatoid arthritis (RA).
 
The secondary objectives are to evaluate the long-term efficacy of filgotinib and to evaluate the long-term effects of filgotinib administration on subject's disability, fatigue, and quality of life.

Study Design:	This will be an open-label, long-term follow-up safety and efficacy study in subjects with RA. Subjects will be enrolled in the study after they have completed one of the 2 core studies (GLPG0634-CL-203 or GLPG0634-CL-204) if, in the opinion of the investigator, they will continue to benefit from treatment in the extension study. Subjects will start the study at the same dose level (filgotinib 200 mg per day), administered in the same dosing regimen (frequency of intake of active IMP) as during the preceding core study (200 mg once daily [q.d.] or 100 mg twice daily [b.i.d.]).
Number of Subjects:	739 subjects

- Treatment:** All subjects will start the study at the same dose level (filgotinib 200 mg per day) either as 200 mg q.d. or as 100 mg b.i.d. The investigator may decide to decrease the daily dose of filgotinib to 100 mg q.d. in case of intolerance or for safety reasons. Subjects will return to filgotinib 200 mg per day after the reasons for decreasing the dose have resolved, and at the investigator's discretion. Subjects can also continue filgotinib 100 mg q.d. when deemed necessary by the investigator.
- Study Duration:** Ongoing until marketing, local (if applicable) regulatory and/or pertinent local reimbursement approval.
- Study Population:** Main inclusion criteria:
- Male or female subjects who are ≥18 years of age, having completed one of the qualifying core studies (GLPG0634-CL-203 or GLPG0634-CL-204) and, who in the opinion of the investigator, will continue to benefit from treatment in the extension study.
- Main exclusion criteria:
- Subjects who have been prematurely withdrawn from one of the 2 core studies (GLPG0634-CL-203 and GLPG0634-CL-204), for any reason including fulfilling the individual stopping criteria.
 - Subjects who are deemed not to be benefiting from the study medication based upon lack of improvement or worsening of their symptoms. Local guidelines for subject treatment to be followed.

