 - Subjects with persistent abnormal laboratory values associated with the use of the study medication (including but not limited to hematology, liver and renal function values) during one of the 2 core studies (GLPG0634-CL-203 or GLPG0634-CL-204), according to the investigator's clinical judgment.
 - Subjects with diagnosis since the inclusion to GLPG0634-CL-203 or GLPG0634-CL-204 core studies of rheumatic autoimmune disease or inflammatory joint disease other than RA, except for secondary Sjögren's syndrome.
- Primary Endpoint:** Safety and tolerability of long-term dosing of filgotinib 200 mg q.d. and 100 mg b.i.d.

- Secondary Endpoints:** Evolution in the percentage of subjects achieving American College of Rheumatology (ACR)20, ACR50, ACR70, and ACR-N responses; European League Against Rheumatism (EULAR) responses; ACR/EULAR remission, clinical disease activity index (CDAI), simplified disease activity index (SDAI), and the disease-activity score based on 28 joints (DAS28 c-reactive protein [CRP]) every 12 weeks or until the Final Visit or the Early Discontinuation Visit (EDV). Change from Baseline in the Quality of Life (functional assessment of chronic illness therapy [FACIT] fatigue scale and 36-item short form health survey [SF-36] scores) every 48 weeks or until the Final Visit or the EDV.
- Safety Analysis:** The safety analysis will be performed for all subjects who used the study medication at least once in this study. Assessment of treatment-emergent adverse events, and of changes from Baseline in laboratory parameters, vital signs, physical examination, and electrocardiograms.
- Efficacy Analysis:** ACR20, ACR50, ACR70, ACR-N, EULAR response, and ACR/EULAR remission, DAS28(CRP), components of the ACR, and DAS28, CDAI, SDAI, and Quality of Life data (FACIT fatigue scale and SF-36 questionnaire) at each post dosing visit (as appropriate) will be analyzed descriptively. Changes from Baseline will be examined to check for evolution over time in treatment effect.

4 Table of Contents

1	Protocol Approval Signatures	2
2	Study Personnel	3
3	Synopsis	4
4	Table of Contents	7
	LIST OF TABLES	9
5	List of Abbreviations and Definition of Terms	10
6	Introduction	12
6.1	Rheumatoid Arthritis	12
6.2	Background on Filgotinib	13
6.3	Background - Pre-clinical Studies	13
6.3.1	Physical, Chemical and Pharmaceutical Properties and Formulations	13
6.3.2	Nonclinical Pharmacology	14
6.3.2.1	Primary and Secondary Pharmacology	14
6.3.2.2	Safety Pharmacology	14

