- Filgotinib 100 mg q.d.: 1 tablet of 100 mg filgotinib in the morning, for subjects decreasing the dose to 100 mg q.d. in the case of intolerance or safety reasons. Subjects can return to the 200 mg daily dose after the reasons for decreasing the dose have resolved, and at the investigator's discretion. Subjects can continue filgotinib 100 mg q.d. when deemed necessary by the investigator.

8.6.2 **Identity of Investigational Products**

The filgotinib study medication is provided as 100 mg strength tablets. Filgotinib HCl salt tablets are presented as an oral film-coated tablet containing filgotinib as HCl salt equivalent to 100 mg of filgotinib, microcrystalline cellulose, crospovidone, colloidal silicon dioxide and glycerol dibehenate. The tablets are coated with a nonfunctional film-coating using Opadry® II coating powder.

Filgotinib maleate salt tablets, 100 mg are beige, debossed with “GSI” on one side and “100” on the other, capsule-shaped, biconvex, film-coated tablets for clinical use. Each tablet contains the equivalent of 100 mg filgotinib free base in the form of filgotinib maleate. In addition to the active ingredient, filgotinib tablets contain the following inactive ingredients: microcrystalline cellulose, lactose monohydrate, fumaric acid, pregelatinized starch, silicon dioxide, magnesium stearate, macrogol/PEG 3350, polyvinyl alcohol, talc, titanium dioxide, iron oxide yellow, and iron oxide red.

8.6.3 **Packaging, Labelling and Distribution**

Filgotinib 100 mg HCl salt tablets are packaged in high density polyethylene (HDPE) bottles with a polypropylene closure and grouped in a carton box for shipment.

Filgotinib 100 mg maleate salt tablets are packaged in white, HDPE bottles. Each bottle contains 30 tablets, silica gel desiccant and polyester packing material. Each bottle is enclosed with a white, continuous thread, child-resistant polypropylene screw cap fitted with an induction-sealed, aluminium-faced liner.

Study drugs to be distributed to centers in the US and other participating countries shall be labeled to meet applicable requirements of the United States Food and Drug Administration (FDA), EU Guideline to Good Manufacturing Practice – Annex 13 (Investigational Medicinal Products), and/or other local regulations.

Filgotinib 100 mg tablets should be stored at controlled room temperature of 25°C (77°F); excursions are permitted between 15°C and 30°C (59°F to 86°F). Storage conditions are specified on the label.

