In case of temperature excursions (outside the permitted range mentioned above), the sponsor should immediately be contacted for evaluation of the excursion and further use of the study drug.

Until dispensed to the subjects, all drug products should be stored in a securely locked area, accessible only to authorized site personnel. To ensure the stability of the study drug and to ensure proper product identification, the drug product should not be stored in a container other than the container in which it is supplied.

Consideration should be given to handling, preparation, and disposal through measures that minimize drug contact with the body. Appropriate precautions should be followed to avoid direct eye contact or exposure when handling.

8.6.4 **Method of Assigning Subjects to Treatment Groups**

Following completion of one of the previous core studies (GLPG0634-CL-203 or GLPG0634-CL-204), subjects who are deemed by the investigator to benefit from continued therapy with study medication, will be offered the option to enter this Long-term Follow-up study. All subjects who opt to roll over into this study will be enrolled and will start the study at the same dose (filgotinib 200 mg daily, administered as either 200 mg q.d. or as 100 mg b.i.d., depending on the q.d./b.i.d. regimen of the preceding core study). Subjects who were on 24 weeks of placebo during the core study

GLPG0634-CL-203 will be randomly assigned to either 100 mg b.i.d. or 200 mg q.d. All other subjects will switch to 200 mg daily, keeping the same regimen (q.d. or b.i.d.) they had in the preceding core study.

This will be done according to a pre-specified randomization scheme prepared by an independent statistician within [REDACTED]. Upon qualification for the study, subjects will be randomized using a computerized interactive voice/web response system (IXRS) [REDACTED] to filgotinib 200 mg q.d. or 100 mg b.i.d. in a 1:1 ratio.

For each subject at each visit, the clinic will contact the IXRS system and will be given the appropriate kit number to be dispensed. The kit will contain the relevant study medication until the next visit.

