3.2. Subject Grouping

For analyses based on the FAS subjects will be grouped according to the treatment to which they were randomized or assigned in GLPG0634-CL-205. For analyses based on the Safety Analysis Set, subjects will be grouped according to actual treatment received in GLPG0634-CL-205. The actual treatment received will differ from the randomized treatment only when their actual treatment differs from randomized treatment for the entire GLPG0634-CL-205 treatment duration.

Subjects will be presented by the following groups:

- Filgotinib with MTX
- Filgotinib monotherapy

The filgotinib with MTX group includes subjects who were from GLPG0634-CL-203 and randomized or assigned to filgotinib 100 mg q.d., filgotinib 100 mg b.i.d. or filgotinib 200 mg q.d. in GLPG0634-CL-205. The filgotinib monotherapy group includes subjects who were from GLPG0634-CL-204 and randomized or assigned to filgotinib 100 mg q.d., filgotinib 100 mg b.i.d. or filgotinib 200 mg q.d. in GLPG0634-CL-205.

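### The SAP describes a 100 mg q.d. limit for US males that the protocol does not contain, and no planned table separates subjects assigned that dose from those on 200 mg per day

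*SAP*

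**What the plan says.** **Protocol.** The synopsis, under Treatment, says "All subjects will start the study at the same dose level (filgotinib 200 mg per day", given as 200 mg q.d. or 100 mg b.i.d. Sections 6.7 and 8.1 agree, with no exception by sex or country. On assignment, section 8.6.4 first deals with subjects who had 24 weeks of placebo in GLPG0634-CL-203, who are randomized between the two regimens. It then adds: "All other subjects will switch to 200 mg daily, keeping the same regimen (q.d. or b.i.d.) they had in the preceding core study". Section 8.6.1 lists 100 mg q.d. among the doses to be evaluated, but only "for subjects decreasing the dose to 100 mg q.d. in the case of intolerance or safety reasons"; section 8.6.6 treats it the same way. The synopsis gives the primary endpoint as "Safety and tolerability of long-term dosing of filgotinib 200 mg q.d. and 100 mg b.i.d".

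**SAP.** Section 1.2 repeats "All subjects will start the study at the same dose level (filgotinib 200 mg daily" and in its next sentence states the US-male limit: "US males were limited to dosing with filgotinib 100 mg q.d. due to an FDA requirement based on a non-clinical testicular toxicity signal". The roll-over table in the same section sends every subject to 200 mg q.d. or 100 mg b.i.d. Section 3.2 then defines the analysis groups: "The filgotinib with MTX group includes subjects who were from GLPG0634-CL-203 and randomized or assigned to filgotinib 100 mg q.d", together with 100 mg b.i.d. and 200 mg q.d. The monotherapy group is built in the same way from GLPG0634-CL-204. Section 7.7 declares no departure from the protocol's safety analyses.

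**The concern.** Two things are at stake.

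- **Which dose was assigned.** The plan does not give one consistent account of the starting dose of US males.
- **What the tables can show.** The primary endpoint is worded for two regimens of 200 mg per day. Subjects assigned half that daily dose sit in the same columns, and no planned table lets a reader see them apart. All subjects under the stated limit are men, and the stated reason for it is a testicular signal. The dilution therefore falls most heavily on the male hormone summaries in SAP 7.2.1, which are the tables closest to that signal.

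**Working it through.** **1. The dose text side by side**

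| Place | Starting dose | Route to 100 mg q.d. |
|---|---|---|
| Protocol synopsis, 6.7, 8.1 text | 200 mg per day, everyone | Investigator reduction only |
| Protocol 8.1 roll-over table | 200 mg q.d. or 100 mg b.i.d. | None |
| Protocol 8.6.1, 8.6.6 | – | Investigator reduction only |
| Protocol 8.6.4 | 200 mg daily | None |
| SAP 1.2 text | 200 mg daily, everyone; then US males at 100 mg q.d. | Regulatory limit, plus investigator reduction |
| SAP 1.2 roll-over table | 200 mg q.d. or 100 mg b.i.d. | None |
| SAP 3.2 | – | Randomized or assigned in GLPG0634-CL-205 |

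The reduction rule does not close the gap. SAP 3.2 speaks of assignment, not of later dose changes. It also reclassifies a subject by actual treatment only if that treatment differed for the whole of GLPG0634-CL-205. Protocol 8.1 sends reduced subjects back to 200 mg once the reason has resolved, at the investigator's discretion. That does not describe a fixed limit by sex and country.

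**2. What the tables separate**

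Adverse event and laboratory summaries, including male hormones, are by treatment group on the Safety Analysis Set. The only groups defined are the two in SAP 3.2. SAP 4.2 summarizes exposure as duration, not dose. Protocol 8.9.1.3 allows a division by mean actual dose as an option; the SAP does not take it up.

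**3. The plan's own figure**

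0.7 × (595 + 280) = 612.5, against 612 stated, so it reproduces. Actual enrolment of 739 is 739/875 = 84.5%. The analyses are descriptive, so the point affects no power calculation or test.

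**4. Size of the dilution**

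The documents give neither the number of US males (k) nor the number of men, so both are assumed. Starting point: 2% to 10% of subjects from the US, 20% of them male, gives 739 × 0.02 × 0.20 ≈ 3 and 739 × 0.10 × 0.20 ≈ 15. A wider range, up to 60, is shown as well.

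- Share of all subjects: f = k/739.
- Share of men, at 20% male overall: k/(0.20 × 739) = k/148.
- Relative change in the pooled rate against the 200 mg rate: f × (r − 1), where r is the event rate at 100 mg relative to 200 mg, with equal exposure. The table uses r = 0.5.

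| k | Share of all | Change, all | Share of men | Change, men |
|---|---|---|---|---|
| 3 | 0.4% | −0.2% | 2.0% | −1.0% |
| 5 | 0.7% | −0.3% | 3.4% | −1.7% |
| 15 | 2.0% | −1.0% | 10.1% | −5.1% |
| 20 | 2.7% | −1.4% | 13.5% | −6.8% |
| 40 | 5.4% | −2.7% | 27.1% | −13.5% |
| 60 | 8.1% | −4.1% | 40.6% | −20.3% |

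With 15% to 25% male, the share of men runs from 2.7% (k = 5, 25% male) to 54% (k = 60, 15% male). The last row is an extreme: at 20% male among US subjects, 60 US men means 60/0.20 = 300 US subjects, or 41% of the trial. These figures are for both groups together; the share within one group could be higher or lower.

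**The case against.** The case on the other side is substantial.

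- **The pooling is open and fits the primary objective.** The objective (protocol 7.1) names filgotinib without a dose, the safety population is everyone dosed, and SAP 3.2 names 100 mg q.d. plainly. A reader might infer that these men are counted as if they had received 200 mg per day. The SAP does not do that: its groups carry no dose label, and it contains no 200 mg per day summary from which they could be removed. This stands, and it is why the pooled groups should stay.
- **Separating these men would not give a clean 200 mg per day column.** Safety baseline and treatment emergence start at the first filgotinib dose, which for many subjects was a lower dose in a core study, and later reductions remain in the groups. This stands too; a split by assigned dose improves the display but does not isolate exposure.
- **Versions differ.** The SAP rests on protocol Amendment 3; the protocol supplied is Amendment 4. A version difference or a country-specific document may explain the conflict. Neither document cites one, and the part of the Amendment 4 change summary available to me does not mention such a limit, which is not conclusive.
- **A general rule followed by an exception is ordinary drafting.** That softens the clash between the two sentences of SAP 1.2. It does not explain the roll-over table, or the protocol's silence.
- **Sites.** A reader might infer that US sites are now starting men on a dose that a regulator had ruled out. The documents do not support that: the protocol reports enrolment of 739 as completed, the SAP puts the limit in the past tense, IXRS allocates the kit at each visit, and SAP 1.2 is background for the analysis rather than a dosing instruction.

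**Conclusion.** The inconsistency is real and should be corrected. The SAP states a dose limit for US males that the supplied protocol does not contain and that the SAP's own roll-over table does not show. Subjects assigned the lower dose are then merged with both 200 mg per day regimens, although the primary endpoint names only those regimens and SAP 7.7 reports no departure.

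The statistical consequence is limited and cannot be fixed exactly, because the number of US males is unknown. With 3 to 15 such men and an event rate half that at 200 mg, the overall pooled rate would be 0.2% to 1.0% lower in relative terms, and a rate among men 1% to 5% lower if 20% of subjects are male. Larger counts would matter mainly for the male hormone tables. It would go too far to conclude that the primary safety result is materially biased: the documents give no count to support that, and no test or decision rule depends on it. The documents do not settle which dose text is correct, and I take no view on it.

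**What to change.** 1. Reconcile the dose text so that both documents state the same dosing for US males: protocol synopsis, 6.7, 8.1 (text and roll-over table), 8.6.1, 8.6.4 and 8.6.6; SAP 1.2 (text and roll-over table) and 3.2. The sponsor decides which text is correct. If a country-specific document or another protocol version is the source, cite it.
2. Report how many subjects were assigned 100 mg q.d. at entry to GLPG0634-CL-205.
3. Keep the two pooled groups. Add descriptive summaries by dose assigned in GLPG0634-CL-205 (100 mg q.d. against 200 mg per day) for the key treatment-emergent adverse event tables and the male hormone tables. Footnote that core-study doses and later reductions still mix exposure within each column.
4. Update SAP 7.7 to record the assignment to 100 mg q.d. and the added summaries.

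The cost is wording in both documents and a few extra columns in selected tables. Some cells will be small, possibly single digits, and should be read descriptively.
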